#### **4.5 Sample Handling and Management**

Study specimens will be accessioned into the EDP Biotech Corp. system using assigned unique identifying number to facilitate tracking and identification during analysis. A visual inspection (in person or via online observation) of the specimens will be made to ensure the specimens meet study requirements for proper appearance.

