## 4.0 Study Design

This is a clinical study to evaluate the feasibility of using anterior nasal (AN) swabs on Rapid SARS-CoV-2 Antigen Test kits for OTC use in symptomatic and asymptomatic individuals following recommendations from the FDA's July 29, 2020 Template for Manufacturers of Molecular and Antigen Diagnostic COVID-19 Tests for Non-Laboratory Use, Section J 7. EDP Biotech Corp. will recruit subjects for an at home human usability study through the internet as well as by referral throughout the United States. Rapid SARS-CoV-2 Antigen Test specimen collection and testing will be done under the supervision of EDP Biotech Corp. either in person or via video conference. Testing will be observed by EDP Biotech Corp. medical professionals or designees either in person or via video conference. The study subjects shall perform the entire workflow including sample collection, testing, and results interpretation. Following results interpretation, subjects will complete a usability and ease of use questionnaires. The data collected in study may be submitted as a regulatory filing to the US FDA or other agencies. All specimens will be collected from participating consenting subjects. Additional testing of the specimens for research purposes may be performed. The study acceptance criteria is a 95% success rate for subjects producing the control line on the Rapid SARS-CoV-2 Antigen Test and a SUS average score of 68 or greater.

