### 4.3 Specimen Collection

Each potential subject will be asked to complete a form describing any symptoms of respiratory illness being experienced, education level, and basic demographics (Appendices 2 and 3). Subjects will be observed by EDP Biotech Corp. personnel or

designees during sample collection, testing, and shipment preparation either in person or via video conference.

Each study volunteer who agrees to participate in the study will be asked to complete an Informed Consent Form (Appendix 6). A parent or guardian will need to consent for subjects under 18 years old. Study subjects between the ages of 7 and 17 years old will be asked to complete an Assent form (Appendix 7). Specimens will be collected and tested only after the Informed Consent form is completed. Each study volunteer will be assigned a unique specimen identification number (SID). The Clinical Investigators or designees will observe AN swab collection and testing. Subjects will collect AN swab samples and perform the Rapid SARS-CoV-2 Antigen Test using only the IFU for instruction or video linked from the IFU. The collection devices and storage tubes will be appropriately labeled with the SIDs and not the names of the participants to maintain confidentiality.

Rapid SARS-CoV-2 Antigen Test AN swab specimens will be collected and tested per the product directions that accompany the device (Appendix 1). Following Rapid SARS-CoV-2 Antigen Test, subjects will complete a System Usability Scale questionnaire (Appendix 4) and an Ease of Use assessment including interpretation of mock test cassettes (Appendix 5).

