## 5.6 Assay Testing

Testing of the study specimens will be performed as follows.

AN swab specimens will be evaluated at the time of collection by study subjects observed by EDP Biotech Corp. personnel either in person or via video conference (Appendix 6). Testing will be performed according to the specific EDP Biotech Corp. Standard Operating Procedures associated with this test. Specimens will be tested per specimen stability parameters in the product instructions (Appendix 1). There is no specific requirement to run a pre-defined number of specimens per run.

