### **6.3 Data Analysis**

#### **6.3.1 Acceptance Criteria for Method Comparison**

The study sponsor will ensure that all specimens are analyzed appropriately, and results are accurately transcribed to an excel spreadsheet for analysis.

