## 10.0 Study Master File (SMF)

The Clinical Investigator (CI) or Designee(s) will collect and review copies of the required essential documents (ED) listed below in the form of a Study Master File (SMF). EDP Biotech Corp. is the sponsor of the study and will maintain the SMF and copies of the required EDs; the Investigator Site File (ISF) will contain original documents.

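### Do the inspection in section 4.5 and the sponsor's duty in section 6.3.1 oblige staff to step into a test that subjects should do from the IFU alone?

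*Protocol*

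**What the plan says.** Section 4.0 states: "The study subjects shall perform the entire workflow including sample collection, testing, and results interpretation". The same section adds that "specimen collection and testing will be done under the supervision of EDP Biotech Corp. either in person or via video conference". Section 4.3 limits what may guide the tester, who works "using only the IFU for instruction or video linked from the IFU", and gives company staff or designees the role of observers.

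Three other sections bear on what staff do:

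- Section 4.5 provides that a "visual inspection (in person or via online observation) of the specimens will be made to ensure the specimens meet study requirements for proper appearance".
- Section 6.3.1, under Data Analysis, reads: "The study sponsor will ensure that all specimens are analyzed appropriately, and results are accurately transcribed to an excel spreadsheet for analysis".
- Section 5.6 says that "AN swab specimens will be evaluated at the time of collection by study subjects observed by EDP Biotech Corp. personnel", and then places testing under the company's SOPs for this test.

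Section 10.0 confirms that "EDP Biotech Corp. is the sponsor of the study", so the sponsor and the observers belong to one company. Section 4.0 also sets the criterion at stake: "The study acceptance criteria is a 95% success rate for subjects producing the control line on the Rapid SARS-CoV-2 Antigen Test". A mean SUS score of at least 68 is required as well.

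**The concern.** Section 2.2 makes the clarity and robustness of the instructions the main focus, so the result is informative only if user errors are allowed to run their course. Read literally, to ensure that every specimen looks right, or that every specimen is analyzed appropriately, means acting when one is not. The specimen is tested as it is collected (5.6), so an inspection made in person or online falls within the observed session, when action is still possible. Testing under company SOPs also sits awkwardly with a tester limited to the IFU or its video.

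Section 1.4 treats the control line as evidence of adequate volume and wicking. A volume error that staff prevented would therefore count directly towards the 95% criterion. A corrected swabbing error might leave the control line unchanged and still hide a weakness in the instructions. A correction made in order to carry out 4.5 or 6.3.1 might also not be seen as a protocol deviation, and so might be missing from the section 6.2 report.

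**Working it through.** **1. The sections side by side**

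| Section | What it fixes | Does it require staff to intervene? |
|---|---|---|
| 4.0 | Subjects do the whole workflow, under company supervision | No. It does not say unaided, but it does not call for help either |
| 4.3 | IFU or linked video only; staff observe | No. It points the other way |
| 4.5 | Specimens are inspected for appearance | No. The sentence is passive, names no actor and states no consequence |
| 5.6 | Subjects test, staff observe, company SOPs apply | Not stated. The SOPs are not limited to observers, but the List of Appendices labels the IFU as Appendix 1 of an SOP |
| 6.3.1 | Sponsor answers for appropriate analysis and accurate transcription | No. It is a general quality sentence under Data Analysis |

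Section 6.3.1 cannot be a guarantee that every user succeeds. The 95% criterion in 4.0 tolerates failures, and 6.2.5 provides for invalid results. The simplest meaning of appropriate analysis is analysis as the protocol prescribes, which under 4.3 means by the IFU or its video. Section 12.2 describes the sponsor's role in the same terms, as seeing that the study follows the protocol.

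**2. What intervention would do, if it happened**

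Inputs: 50 self-tests and 50 tests on another person (4.4), so n = 100. The criterion is read as an observed rate of at least 95%, so 0.95 × 100 = 95 control lines are needed.

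| Control lines without intervention | Change | Rate | Criterion |
|---|---|---|---|
| 94 | none | 94/100 = 94.00% | not met |
| 94 | 1 failure prevented | 95/100 = 95.00% | met |
| 94 | 1 failed test dropped | 94/99 = 94.95% | not met |
| 94 | 2 failed tests dropped | 94/98 = 95.92% | met |
| 93 | 2 failures prevented | 95/100 = 95.00% | met |
| 93 | 2 failed tests dropped | 93/98 = 94.90% | not met |
| 93 | 3 failed tests dropped | 93/97 = 95.88% | met |

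Under assumed rates, let p be the true unaided success rate and c the share of failures that staff prevent. Then q = p + (1 − p)c, and the chance of meeting the criterion is P(X ≥ 95) with X ~ Binomial(100, q). For p = 0.90:

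- c = 0: q = 0.900, chance 5.8%
- c = 0.25: q = 0.925, chance 23.1%
- c = 0.50: q = 0.950, chance 61.6%

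The documents give neither p nor c, so these figures only show that routine coaching would matter.

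**3. Whether the cited sections produce these cases**

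- *Prevented failures* need staff to correct a tester. No section tells them to, and 4.3 confines instruction to the IFU and its video.
- *Dropped tests* are tests without a control line. If these count as invalid, as the procedural-control role in 1.4 suggests, then 6.2.1, 6.2.2 and 6.2.5 already govern their exclusion and repetition. The shift from 94/100 to 94/98 is then not an effect of 4.5 or 6.3.1.
- *Specimen appearance* is not linked to the control line by any section, so 4.5 has no shown route to the criterion.
- *Reporting:* a test rejected on inspection is an excluded result. Section 6.2.2 requires the reason to be documented and the cases summarised.

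**The case for a change.** The best case for a change is that the protocol never tells staff to stay silent. Section 4.4 does bar a parent from intervening when a 14- to 17-year-old tests, so its authors knew that intervention matters, yet staff face no equivalent bar and 4.0 speaks of supervision. Two observers could follow the same text, one silent and one prompting, and both claim compliance. If 6.3.1 concerned only data handling, its first clause would add little to the second. Section 5.6, taken literally, has subjects testing by company SOPs, which does not match 4.3. Clarifying all this would cost a few words.

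Part of this stands. The language in 4.5 and 6.3.1 is loose, 5.6 does not limit its SOPs to observers, and help given to a tester is not named as an item to record. What does not stand is the step from loose wording to conflicting duties. A prompting observer would be supplying instruction beyond the IFU and its video, which 4.3 excludes. That is a deviation, and 6.2 requires deviations to be described. The SOPs are not available here, and because the IFU is listed as an SOP appendix, testing by the SOP may simply mean testing by the IFU.

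**Conclusion.** The concern does not call for a change to the plan. The conflict is inferred from the verb used in 4.5 and 6.3.1; neither section instructs staff to help, correct or reject. An inspection that only records what is seen, and a sponsor duty confined to conduct according to the protocol and correct transcription, both fit 4.3. Observers who follow 4.3 as written produce a sound assessment of the instructions and breach nothing in 4.5, 5.6 or 6.3.1.

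No pass/fail reversal can be attributed to these sections. The 94-to-95 example needs coaching that the protocol does not prescribe, and the dropped-test examples overlap with the invalid-result rules. The conclusion rests on two assumptions: that staff treat 4.3 as the rule for the session, and that the SOPs cited in 5.6 do not direct staff to assist the tester. What remains is imprecise wording, chiefly in 5.6, which a competent study team would resolve in observer training in the sense of 4.3.

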### **5.0 Sample Preparation and Testing Procedure**

#### **5.1 Instrument Set-Up (Calibration and Quality Control)**

All lateral flow kit quality controls and instrument quality control and calibration procedures will be performed per manufacturer's recommendations or the laboratory's QA/QC manual, as appropriate. Instrument calibration and instrument performance will be documented on each day that testing is performed. All documentation related to the operation of the instrument will be completed, verified and recorded per the laboratory's standard procedures.

#### **5.2 Reagent Preparation**

All reagents will be prepared for use by lateral flow kit manufacturer or EDP Biotech Corp. laboratory personnel, as appropriate or as specified in their respective manufacturer's package insert/instruction for use documents.

#### **5.3 Specimen Processing**

Individuals participating in the usability study will process their own specimens or specimens of another individual, as appropriate, at the time of enrollment and testing EDP Biotech Corp personnel will process the collected AN swab specimen data as it is generated.

#### **5.4 Sample Preparation**

SARS-CoV-2 antigen will be extracted from the collected specimens using procedures provided by the investigational lateral flow kit manufacturers. The specifications for specimen integrity described in the manufacturer's instrument instructions will be followed, i.e., storage conditions prior to testing.

#### **5.5 Control/Calibrator Preparation**

Assay controls will be included in each test run per manufacturers' directions.

## 5.6 Assay Testing

Testing of the study specimens will be performed as follows.

AN swab specimens will be evaluated at the time of collection by study subjects observed by EDP Biotech Corp. personnel either in person or via video conference (Appendix 6). Testing will be performed according to the specific EDP Biotech Corp. Standard Operating Procedures associated with this test. Specimens will be tested per specimen stability parameters in the product instructions (Appendix 1). There is no specific requirement to run a pre-defined number of specimens per run.

## 5.7 Reporting of Results

The results obtained with the Rapid SARS-CoV-2 Antigen Test will be captured electronically in the EDP Biotech Corp. LIMS system by observers.

# 6.0 Data Management and Analysis

## 6.1 Sample ID Numbers and Identification

Each sample entered into the study will be assigned the study sample number during accessioning. A data management log listing each sample number and storage information will be maintained.

## 6.2 Data Evaluation and Accessibility

A report tabulating and analyzing the data will be prepared by the Clinical Investigator including tables of the results and a description of any deviations from the protocol.

### 6.2.1 Acceptability of Data for Analysis

Valid individual specimen results generated in invalid runs are not acceptable for inclusion in final data analysis. Samples tested in invalid runs must be re-tested if the remaining specimen volume is available. Only valid results from specimens in valid runs will be included in the final data analysis.

### 6.2.2 Exclusion of Data from Analysis

Data from invalid runs results will be excluded. All excluded results will be documented with rationale for exclusion and a summary of these cases will be provided.

### 6.2.3 Data Entry and Corrections to Study Documents

All entries must be legible and made in indelible ink (preferably black); do not use pencil. Strike incorrect entries with a single line (do not obliterate or put "white-out" on the original entry). Then enter the correct information next to the original entry, initial, and date the correction.

#### **6.2.4 Assay Run Data**

Any Printouts corresponding to assay runs will be maintained and a copy placed in a study binder. A record will be maintained regarding assay reagents and calibrators by lot number and expiration date.

#### **6.2.5 Invalid Results**

Invalid results will be repeated either by the same subject or a different subject until the criteria found in section 4.4 is met.

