### 1.4 Principles of the Device

The COVID-19 Antigen Rapid Test Device detects SARS-CoV-2 viral antigens through visual interpretation of color development. Anti-SARS-CoV-2 antibodies

are immobilized on the test region of the nitrocellulose membrane. Anti-SARS-CoV-2 antibodies conjugated to colored particles are immobilized on the conjugated pad. A sample is added to the extraction buffer which is optimized to release the SARS-CoV-2 antigens from specimen. During testing, the extracted antigens bind to anti-SARS-CoV-2 antibodies conjugated to colored particles. As the specimen migrates along the strip by capillary action and interacts with reagents on the membrane, the complex will be captured by the anti-SARS-CoV-2 antibodies at the test region. Excess colored particles are captured at the internal control zone. The presence of a colored band in the test region indicates a positive result for the SARS-CoV-2 viral antigens, while its absence indicates a negative result. A colored band at the control region serves as a procedural control, indicating that the proper volume of specimen has been added and membrane wicking is working. (See Appendix 1).

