#### **4.4 Sample Types and Numbers**

Subjects will be enrolled in an “all comers” style, including both symptomatic and asymptomatic patients. The study population will include subjects from 2 years old to greater than 65 years old. Minors must be consented by their parent or legal guardian. The parent or legal guardian should collect the samples and perform testing if the child is between 2 and 13 years old. Older children ages 14-17 should collect their samples and perform their tests without their parent or legal guardian intervening. The study will include two sections, 50 subjects testing themselves and 50 subjects testing another person such as children between the ages of 2 and 13 years old. Enrollment efforts in various zip codes will be pursued in order to represent different socioeconomic and educational backgrounds and this information will be captured in the tester questionnaire (Appendix 2) and subject questionnaire (Appendix 3). A portion of the study population should include Spanish speaking users. High risk individuals will not be excluded. Participants who regularly use home diagnostic tests, such as glucose meters, will be excluded. Study testing will continue until the full range of 2-65+ ages are tested including at least 50 self-tests and 50 tests performed by subjects on other participants.

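### The invalid-result rules remove and replace the failures that the 95% control-line criterion is meant to count, so on the natural reading that criterion cannot fail

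*Protocol*

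**What the plan says.** - Protocol section 4.0 (Study Design) accepts the device on two conditions: a "95% success rate for subjects producing the control line on the Rapid SARS-CoV-2 Antigen Test and a SUS average score of 68 or greater". It does not say which attempt counts or what the denominator is.
- Section 1.4 (Principles of the Device) explains that the control band "serves as a procedural control, indicating that the proper volume of specimen has been added and membrane wicking is working".
- Section 6.2.1 (Acceptability of Data for Analysis) closes with: "Only valid results from specimens in valid runs will be included in the final data analysis".
- Section 6.2.2 (Exclusion of Data from Analysis) excludes data from invalid runs and adds: "All excluded results will be documented with rationale for exclusion and a summary of these cases will be provided".
- Section 6.2.5 (Invalid Results) states: "Invalid results will be repeated either by the same subject or a different subject until the criteria found in section 4.4 is met".
- Section 4.4 (Sample Types and Numbers) continues testing until the full age range is covered, "including at least 50 self-tests and 50 tests performed by subjects on other participants". It sets no upper limit on attempts.
- On who tests and how, section 4.4 states: "Participants who regularly use home diagnostic tests, such as glucose meters, will be excluded". Section 4.3 (Specimen Collection) has subjects work "using only the IFU for instruction or video linked from the IFU".

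**The concern.** The control-line criterion measures whether lay users can run the test correctly. Its failure event is a card that shows no control line. The same event makes the card invalid in the ordinary sense, and the data rules in section 6.2 take invalid results out of the analysis and have them repeated. If those rules apply to this endpoint, every failure is removed and a success put in its place.

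The stated main focus (section 2.2) is how clear and robust the instructions are, and section 9.0 intends the results to show suitability for home use without a prescription. A user who follows the instructions and gets no control line is direct evidence on that question.

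A repeat by the same subject adds a second problem. The design aims at users without regular home-test experience who have only the IFU or its linked video. Someone repeating a failed test has already run it once, under observation.

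**Working it through.** The protocol gives no power figure or sample-size derivation, so there is nothing of that kind to reproduce.

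**Inputs**
- Threshold 95% (section 4.0) and planned tests 50 + 50 = 100 (section 4.4). A pass therefore needs at least 0.95 × 100 = 95 successes.
- True first-attempt control-line rate p: not in the protocol. Assumed range 0.80 to 0.98.
- Success probability r of a repeat after a first failure: not in the protocol. Assumed 0.4 to 0.9.
- One test per tester and independence between testers are assumed.

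**1. Rules as written, on the natural reading.** Invalid cards are dropped and replaced until 100 valid results exist. The rate is 100/100 = 100% for every p above 0, and P(pass) = 1.

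Mean attempts needed are 100/p. The number of failures before the 100th success is negative binomial.

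| p | Mean attempts | Mean failures outside the rate | 5th–95th percentile of failures |
|---|---|---|---|
| 0.80 | 100/0.80 = 125 | 25 | 16–35 |
| 0.90 | 100/0.90 ≈ 111 | 11 | 6–17 |

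**2. First attempts of 100 testers counted, missing line = failure.** P(pass) = P(X ≥ 95), with X ~ Binomial(100, p).

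| p | P(pass) |
|---|---|
| 0.80 | 0.00002 |
| 0.85 | 0.0016 |
| 0.90 | 0.058 |
| 0.95 | 0.62 |
| 0.98 | 0.985 |

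**3. Milder reading: testers stay in the denominator, but one repeat by the same tester may count as success.** The rate becomes p + (1 − p)r, and P(pass) follows from the same binomial.

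| p | r | Rate | P(pass) |
|---|---|---|---|
| 0.80 | 0.4 | 0.80 + 0.20 × 0.4 = 0.88 | 0.015 |
| 0.80 | 0.6 | 0.80 + 0.20 × 0.6 = 0.92 | 0.18 |
| 0.80 | 0.8 (independence) | 0.80 + 0.20 × 0.8 = 0.96 | 0.79 |
| 0.90 | 0.4 | 0.90 + 0.10 × 0.4 = 0.94 | 0.44 |
| 0.90 | 0.9 (independence) | 0.90 + 0.10 × 0.9 = 0.99 | 0.999 |

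**4. Every card counted, until 100 are valid.** With f failures the rate is 100/(100 + f). Since 100/105 = 95.2% and 100/106 = 94.3%, a pass allows at most 5 failures. The negative binomial gives P(pass) below 0.0001 at p = 0.80 and 0.042 at p = 0.90.

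At a true rate of 0.90 the chance of passing is thus 0.042, 0.058, 0.44 to 0.999, or 1, depending only on how failed attempts are treated. The only treatment that the protocol's own rules spell out is the one that gives 1.

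**The case against.** The protocol never says that a card without a control line is an invalid result, and the IFU, where a definition would be expected, is not shown. Section 4.0 speaks of a success rate among subjects, which presupposes that failures are counted. Sections 6.2.1 and 6.2.2 use laboratory language (runs, remaining specimen volume) and could be meant for the antigen result alone. Section 6.2.5 orders a repeat but does not itself delete the first attempt, and the 50 + 50 quota is a minimum. Section 6.2.2 keeps exclusions visible. The choice of denominator could also be left to an SAP. Finally, one failed attempt is not regular use of home tests, and a repeat with the same IFU does not breach section 4.3.

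Some of this stands:
- The meaning of an invalid result is inferred. Invalid runs may well mean failed control runs, so the conflict rests mainly on the last sentence of section 6.2.1 together with section 6.2.5.
- A reader could rebuild the first-attempt rate from the summary of exclusions.
- A repeat breaks no eligibility or instruction rule. It only fits poorly with a study of first-time use.

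The rest does not remove the problem. No text limits section 6.2 to the antigen result or keeps failures in the rate. The last sentence of section 6.2.1 requires a valid result as well as a valid run, so reading a run as a control batch does not bring back a card that is itself invalid. The summary of exclusions does not return failures to the rate. Nor is this only detail left to an SAP: the protocol states the exclusion and repeat rules, and an SAP would have to override them.

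**Conclusion.** The concern holds. On the natural reading, the analysed control-line rate is 100% by construction and the 95% threshold decides nothing. At an assumed first-attempt rate of 0.80 the criterion would be met with on average 25 failures left out, although a first-attempt count would pass with probability of only 0.00002. At 0.90 the comparison is certainty against 0.058.

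The conclusion rests on treating a card without a control line as an invalid result, which section 1.4 supports but no passage states. The true rates and repeat-success values are assumptions, but the 100% result does not depend on them. It concerns the control-line criterion only: the SUS criterion can still fail. It must be corrected because one of the study's two acceptance criteria is neutralised.

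**What to change.** In section 4.0, define the denominator of the 95% rate as the first attempt of every enrolled tester who starts a test, and score a missing control line on that attempt as a failure. In addition:

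- Count the 50 + 50 quota for this endpoint in first attempts, valid or not.
- State that sections 6.2.1, 6.2.2 and 6.2.5 do not apply to this endpoint, and define both an invalid result and an invalid run.
- Report repeat attempts separately, never in place of the first attempt.
- Show documented kit defects, for example a pouch damaged on receipt, in a sensitivity analysis.

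The cost is protocol wording only, with no extra subjects. The reported control-line rate will be less favourable, and the criterion can then fail.
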